4.1 Study Population

- Phase 1 Interviews: Bereaved Caregiver subjects will be caregivers of patients who died in the past year with a primary diagnoses of GI or lung cancers. Clinician subjects will be oncologists, palliative care physicians, nurses, nurse practitioners, social workers, or psychologists who care for patients with metastatic GI and lung cancers.
- Phase 2: Patient subjects will be adults (18+) diagnosed with lung or GI cancer, with a progression of their disease after one line of therapy. Clinician subjects will be Lung, Head and Neck, or GI oncologists. All subjects' primary language will be English and will have full mental capacity.

4.2 Inclusion Criteria

Phase 1 Interviews:

Bereaved Caregivers:

1. Caregivers of patients who died in the past year with a primary diagnoses of GI or lung cancer
2. Fluent in English

Clinicians:

1. Currently care for patients with metastatic GI and lung cancers as an oncologist, palliative care physician, nurse, nurse practitioner, social worker, or psychologist

Phase 2:

Patients:

1. Male or female \geq 18 years of age.
2. Receiving ongoing care (\geq 2 visits) that includes regular scans
3. Progression on at least 1 line of systemic cancer therapy
4. Prognosis from an oncologist of less than 12 months
5. Receiving care from an oncologist participating in the Oncolo-GIST study
6. Fluent in English

Clinicians:

1. Specialize in Lung, Head and Neck, and GI cancers
2. Currently provide care at the WCM Lung, Head and Neck, and GI cancer clinics
3. Fluent in English

4.3 Exclusion Criteria

Phase 1 Interviews:

Bereaved Caregivers:

1. Caregivers of patients who died longer than 1 year from the time of enrollment
2. Caregivers of a patient that did not have a primary diagnoses of GI or lung cancer
3. Not fluent in English

Clinicians:

1. Does not currently care for patients with metastatic GI and lung cancers as either an oncologist, palliative care physician, nurse, nurse practitioner, social worker, or psychologist

Phase 2:

Patients:

1. Under 18 years of age
2. Not receiving ongoing cancer care (≥ 2 visits) that includes regular scans
3. Not progressing on at least 1 line of systemic cancer therapy
1. Prognosis from an oncologists of 12 months or more
4. Not receiving care from an oncologist participating in the Oncolo-GIST study
5. Not fluent in English
6. Cognitive impairment, as indicated by a score of <8 on the Short Portable Mental Status Questionnaire or a diagnosis of dementia or a related condition

Clinicians:

1. Does not specialize in Lung, Head and Neck, and GI cancers
2. Does not currently provide care at the WCM Lung, Head and Neck, and GI cancer clinics
3. Not fluent in English

4.4 Strategies for Recruitment and Retention

Phase 1 Interviews: Clinicians and bereaved caregivers will be recruited by targeted sampling. We will use WCM's EPIC system as well request referrals from Weill Cornell Medicine (WCM) clinicians to recruit 10 bereaved caregivers of GI and lung cancer patients who died within the past year.

Trained research co-investigators will screen deceased patients using EPIC after referral. If deemed eligible, caregivers will be contacted by either phone or email by non-clinician co-investigators.

Oncology clinicians including oncologists, palliative care physicians, nurses, nurse practitioners, social workers, and psychologists who care for patients with GI and lung cancer, will be identified for recruitment via convenience and snowball sampling by either phone or email. These clinicians are known by co-investigators and/or their affiliates. Recruitment emails will include an attached flyer. Flyers will also be distributed on WCM/NYP properties. Phone recruitment will be by script and will include information from the flyer. Participants will not be contacted more than twice if there is no response and if at any point, a potential participant asks not to be contacted, study staff members will thank them for their time, and be put on a do not contact list. Participants will receive \$100 compensation via a ClinCard after the interview is completed.

Phase 2: Patients will be identified from weekly reviews of patient charts and discussions with the WCM GI, Head and Neck, and lung clinic staff working alongside [name] and [name], respectively. Trained research assistants (RA) will screen patients at the Lung and GI Clinics for eligibility, using WCM's EPIC system. If deemed eligible (see eligibility and exclusion criteria), the research assistant will approach the patient in clinic, to explain the study, and the study procedures. Flyers will also be distributed on WCM/NYP properties. Patient subjects will receive \$25 compensation via ClinCard after each interview is completed, with a possible total of \$100 by the

end of the study.

- *Anticipated accrual rate*
 - Phase 1 Interviews
 - Recruit and enroll 10 oncology clinicians and 10 bereaved in the 1st 6 months of the study
 - Phase 2
 - Recruit and enroll 50 patients (3/month for ~ 18 months)

5. Registration Procedures

5.1 Subject Registration (WCM only)

Subjects will be registered within the WRG-CT as per the standard operating procedure for Subject Registration.

5.2 Subject Registration (Sub-sites)

Not Applicable

6. Study Procedures

6.1 Schedule of Assessments

Table 1. Schedule of trial events for Phase 1 Interviews (Bereaved Caregivers and Clinicians)

	Pre-study	Visit 1 (Interview)
Screening	X	
Informed Consent (see note)	X	
Review of Oncolo-GIST intervention		X
Demographics		X
Oncology Based Communication Questions		X
Semi-structured Interview		X

Table 2. Schedule of trial events for Phase 2

	Arm	Pre-Study	Pre-Scan	Post-Scan 1 (approx. 1 week)	Post-Scan 2	Post-Scan 3	Post-Scan 4 (up to 12 months)
Short Portable Mental Status Questionnaire ^s	P	X					
Health Literacy Assessment (REALM) ^s	P	X					
Informed Consent	B	X					
Oncolo-GIST Training (Clinicians)	C*	X					
Demographics	P		X				
4 Item Illness Understanding	P		X				
Treatment Intent	P		X				
Treatment Preferences	P		X				
CWC II Psychological questions	P		X				
NCCN Distress Thermometer	P		X				
The Human Connection Scale	P		X	X	X	X	
HADS	P		X	X	X	X	
McGill Quality of Life Questionnaire	P		X	X	X	X	
PSWQ-Ultra Brief	P		X				
PANAS	P		X				
Primary Appraisal Secondary Appraisal (PASA) items (Threat and Challenge subscales only)	P		X				
Post Scan Clinician Questionnaire	C			X			
Medical Chart Abstraction	C				X	X	X
Post Scan Patient Questionnaire	P			X	X	X	
Training Quiz	C*	X					
Post-Study Questionnaire	C						X

C = Clinicians, P = Patients, B = Both, ^s= Screening, * = Intervention Arm Only

Note: The Post-Scan 4 Chart Abstraction will occur when monitoring if progression of the disease is found after Post-Scan 3 or the patient is deceased; up to 12 months.

7.1 Data Reporting / Regulatory Considerations

7.2 Data Collection

The data collection plan for this study is to utilize REDCap to capture all treatment, toxicity, efficacy, and adverse event data for all enrolled subjects.

7.2.1 REDCap

REDCap (Research Electronic Data Capture) is a free data management software system that is fully supported by the Weill-Cornell Medical Center CTSC. It is a tool for the creation of customized, secure data management systems that include Web-based data-entry forms, reporting tools, and a full array of security features including user and group based privileges, authentication using institution LDAP system, with a full audit trail of data manipulation and export procedures. REDCap is maintained on CTSC-owned servers that are backed up nightly and support encrypted (SSL-based) connections. Nationally, the software is developed, enhanced and supported through a multi-institutional consortium led by the Vanderbilt University CTSA.

7.3 Regulatory Considerations

7.3.1 Institutional Review Board/Ethics Committee Approval

As required by local regulations, the Investigator will ensure all legal aspects are covered, and approval of the appropriate regulatory bodies obtained, before study initiation.

Before initiation of the study at each study center, the protocol, the ICF, other written material given to the patients, and any other relevant study documentation will be submitted to the appropriate Ethics Committee. Written approval of the study and all relevant study information must be obtained before the study center can be initiated or the IP is released to the Investigator. Any necessary extensions or renewals of IEC/IRB approval must be obtained for changes to the study, such as amendments to the protocol, the ICF, or other study documentation. The written approval of the IEC/IRB together with the approved ICF must be filed in the study files.

The Investigator will report promptly to the IEC/IRB any new information that may adversely affect the safety of the subjects or the conduct of the study. The Investigator will submit written summaries of the study status to the IEC/IRB as required. On completion of the study, the IEC/IRB will be notified that the study has ended.

All agreed protocol amendments will be clearly recorded on a protocol amendment form and will be signed and dated by the original protocol approving signatories. All protocol amendments will be submitted to the relevant institutional IEC/IRB for approval before implementation, as required by local regulations. The only exception will be when the amendment is necessary to eliminate an immediate hazard to the trial participants. In this case, the necessary action will be taken first, with the relevant protocol amendment following shortly thereafter.

Once protocol amendments or consent form modifications are implemented at the lead site, Weill Cornell Medicine, updated documents will be provided to participating sites. Weill Cornell Medicine must approve all consent form changes prior to local IRB submission.

Relevant study documentation will be submitted to the regulatory authorities of the participating countries, according to local/national requirements, for review and approval before the beginning of the study. On completion of the study, the regulatory authorities will be notified that the study has ended.

7.3.2 Ethical Conduct of the Study

The Investigators and all parties involved should conduct this study in adherence to the ethical principles based on the Declaration of Helsinki, GCP, ICH guidelines and the applicable national and local laws and regulatory requirements.

This study will be conducted under a protocol reviewed and approved by the applicable ethics committees and investigations will be undertaken by scientifically and medically qualified persons, where the benefits of the study are in proportion to the risks.

7.3.3 Informed Consent

The investigator or qualified designee must obtain documented consent according to ICH-GCP and local regulations, as applicable, from each potential subject or each subject's legally authorized representative prior to participating in the research study. Subjects who agree to participate will sign the approved informed consent form and will be provided a copy of the signed document.

The initial ICF, any subsequent revised written ICF and any written information provided to the subject must be approved by IRB prior to use. The ICF will adhere to IRB/IEC requirements, applicable laws and regulations.

7.3.4 Compliance with Trial Registration and Results Posting Requirements

Under the terms of the Food and Drug Administration Modernization Act (FDAMA) and the Food and Drug Administration Amendments Act (FDAAA), the Sponsor-Investigator of the trial is solely responsible for determining whether the trial and its results are subject to the requirements for submission to <http://www.clinicaltrials.gov>. Information posted will allow subjects to identify potentially appropriate trials for their disease conditions and pursue participation by calling a central contact number for further information on appropriate trial locations and trial site contact information.

7.3.5 Record Retention

Essential documents are those documents that individually and collectively permit evaluation of the study and quality of the data produced. After completion of the study, all documents and data relating to the study will be kept in an orderly manner by the Investigator in a secure study file. Essential documents should be retained for 2 years after the final marketing approval in an ICH region or for at least 2 years since the discontinuation of clinical development of the IP. In addition, all subject medical records and other source documentation will be kept for the maximum time permitted by the hospital, institution, or medical practice.

7.3.6 Data Safety and Monitoring Plan

Monitoring

A medical monitor is not appointed for this study as the risk level to participants is extremely low. Patients are only approached with the express approval of their treating oncologist. Furthermore, co-investigator [name] will consult on the suitability of the study for individual patients, when this is in doubt, as well as any unexpected medical events that occur during patients' participation in the study. Participants' responses to study assessments will be monitored for severe psychological distress. Patients' participation will be discontinued if they experience severe distress attributable to the study, as determined by the co-investigators or their treating

physician. Participants may also withdraw from the study at any time with no effect on their treatment.

Reporting to DSMC

Due to the low clinical risk involved in this study, we propose reporting to the Weill Cornell DSMC on an **annual** basis. Annual reports will comprise: recruitment and retention totals, including voluntary patient withdrawals; a summary of progress since the previous DSMC report; and accounts of any and all adverse events (AEs). For the purpose of this study, an AE is defined as a participant experiencing severe psychological distress, regardless of attribution.

8. Statistical Considerations

8.1 Sample Size/Accrual Rate

Phase 1 Interview: Sample size will be 10 clinicians and 10 bereaved caregivers recruited over 6 months.

Phase 2: The pilot clustered RCT will enroll 4 medical oncologists (2 Oncolo-GIST Version 2.0 trained; 2 usual care) and 50 patients (25 will receive care from an Oncolo-GIST Version 2.0-trained oncologist, 25 will receive usual care) within an 18-month recruitment period. Based on past recruitment yields in the GI and lung cancer clinics at WCM (e.g., recruitment of 60 advanced GI cancer patients alone in 18 months), we are confident that we can recruit this number of eligible patients within an 18-month period. Given this is an oncologist communication intervention, we expect the patient drop-out rate to be low. Fifty participants will ensure fairly stable estimates of intervention effects and confidence intervals and indicate if there is a “signal” that the intervention is helpful for promoting prognostic understanding. Using our validated 4-point prognostic understanding score⁴ as a continuous outcome, if Cohen’s d is large (0.8), with 48 patients and 4 oncologists, the power will be $> 80\%$. If the effect size is medium (0.5), power will drop to 30%.

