Outcome will be a training manual for clinicians that teaches the Oncolo-GIST methods of communication. The efficacy of the intervention will be determined by measuring the patient's prognostic understanding using our validated 4-item assessment. The assessment will determine if the patient understood the scan results as well as the expected outcomes of treatments offered. Outcomes will also include whether a DNR order was completed for the patient, the patients quality of life (McGill Quality of Life measure) , patient performance status (e.g., Eastern Cooperative Oncology Group, ECOG), as well as the type care received (e.g., anticancer, intensive, palliative care).

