In Phase 2, for the pilot cluster RCT study (Aim #3), we will recruit adult patients (n=50) with metastatic GI, head and neck, or lung cancers with scan results that reveal progression (worsened disease) on an initial systemic treatment; that is, patients whose life-expectancy can reliably be estimated to be months, not years.^{5 9} Medical oncologists (n=4) who care for these patients will also be consented for study participation and half (n=2) will be randomized to receive the brief "Oncolo-GIST communication" training. The Oncolo-GIST training will provide instruction in how to introduce the topic of prognosis, describe scan results as "worse," prognosis as "likely months, not years," and expected treatment outcomes (e.g., "not expected to be cured by treatment," and expected impact on quality of life – that is, whether the anticancer treatment is likely to make them feel overall better or worse). We expect 12-13 patients will be clustered within each of the 4 oncologists. Hierarchical Linear Modeling (HLM) techniques will be employed to address the non-independence of patient assessments within each cluster. Patients (n=25) will be seen by either an Oncolo-GIST trained oncologist or an oncologist not trained in the intervention; that is, usual care (n=25). Patients in both arms will have met the same eligibility criteria (i.e., have similar prognoses).

Thus, we will get initial feedback on the Oncolo-GIST intervention from relevant stakeholders and key informants, obtain information on the patient and oncologist experience with the intervention and evaluate its feasibility and acceptability. Finally, we will obtain preliminary effect size estimates

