8.3 Analysis of Endpoints

8.3.1 Analysis of Primary Endpoints

Phase 1 Interviews: We will obtain feedback on the current version of Oncolo-GIST (Version 1.0). Morse’s guidelines¹⁵ for rigorous qualitative research (e.g., audit trail, saturation) will be followed and Atlas.ti software used.¹⁶ Themes emerging will be quantified (re: frequency, priority) and considered to inform revisions to the Phase 1 Open Trial Oncolo-GIST intervention.

Phase 2: We will generate preliminary effect size estimates to inform the planning of the larger, efficacy randomized controlled trial (RCT). Hierarchical Linear Modeling (HLM)¹⁷ will be used to evaluate intervention effects. HLM is statistically appropriate because it accounts for the clustering of patients within oncologists, creating nonindependence of clustered assessments. HLM will model oncologists as a random effect as has been done in prior RCTs.^{18 19} Baseline covariates known to affect study outcomes (e.g., patient health literacy) will be included in models to increase the precision of effect size estimates.²⁰ This will provide a preliminary effect size estimate of Oncolo-GIST Version 2.0’s ability to improve patients’ prognostic understanding for a future, larger study. Linear and logistic regression models will estimate effects of the

Oncolo-GIST intervention on secondary and exploratory outcomes.

9. Adverse Event Reporting Requirements

Adverse event (AE) monitoring and reporting is a routine part of clinical research. Safety is monitored by evaluation of adverse events reported by subjects or observed by investigators or research staff, as well as by other investigations such as clinical laboratory tests, x-rays, electrocardiographs, etc.

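### Section 8.1 states power above 80% at d = 0.8 and 30% at d = 0.5 for the same 48 patients and 4 oncologists; no usual test gives both

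*Combined protocol and SAP*

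**What the plan says.** Section 8.1 (Sample Size/Accrual Rate) treats the prognostic understanding score as continuous and gives two powers. For d = 0.8, "with 48 patients and 4 oncologists, the power will be" above 80%. The next sentence reads "If the effect size is medium (0.5), power will drop to 30" percent. Nothing marks a change of design between the two. Just before them the section says: "Fifty participants will ensure fairly stable estimates of intervention effects and confidence intervals".

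Section 3.1 describes the allocation: of four oncologists, "half (n=2) will be randomized to receive the brief" training, with 12–13 patients expected per oncologist. For the analysis, Section 8.3.1 says "HLM will model oncologists as a random effect" and that baseline covariates "will be included in models to increase the precision of effect size estimates". Neither section, nor any other part of the document, gives the alpha, sidedness, intraclass correlation (ICC), covariate R² or degrees of freedom behind the two powers.

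**The concern.** For a fixed design and test, power depends on the effect size only through its ratio to the standard error. Moving from d = 0.5 to d = 0.8 multiplies that ratio by 0.8/0.5 = 1.6. A rise from 30% to more than 80% is too steep for that.

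The two figures are the only quantitative support in 8.1 for expecting Phase 2 to show a signal on the primary outcome. The Endpoints entry of the Protocol Summary says "The efficacy of the intervention will be determined by measuring the" patient's prognostic understanding, and Section 8.3.1 says "We will generate preliminary effect size estimates to inform the planning of the larger" efficacy trial. A reader judging what this pilot can show, or how far to trust its estimate when sizing the next trial, would be relying on figures that cannot both be right.

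**Working it through.** **Inputs from the plan.** 48 patients and 4 oncologists (8.1). Equal allocation gives n = 24 patients and 2 oncologists per arm, so m = 12 per oncologist.

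**Inputs assumed because the plan gives none.** Alpha and sidedness as tabulated; reference distribution normal, t on 46 df (patients: 48 − 2) or t on 2 df (oncologists: 4 − 2); ICC and R² where shown.

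**Formulas**, in SD units: SE = √{2 × [1 + (m − 1) × ICC] × (1 − R²) / n}; noncentrality λ = d/SE; power is the probability that a test statistic with noncentrality λ exceeds its critical value.

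**Step 1: try to reproduce the stated figures** (two-sided 0.05, normal reference, R² = 0).
- ICC 0: SE = √(2/24) = 0.289. Power is 79.1% at d = 0.8 and 41.0% at d = 0.5. With 25 per arm: 80.7% and 42.4%.
- ICC 0.05: SE = √(2 × 1.55/24) = 0.359. Power is 60.5% and 28.5%.

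The first setting comes near the 80% and misses the 30%; the second does the opposite.

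**Step 2: remove the unknowns.** ICC, R² and n enter only through SE, which both powers share. So solve for the SE that gives 30% at d = 0.5 and use it at d = 0.8. At two-sided 0.05 with a normal reference, SE = 0.3485, λ(0.5) = 0.5/0.3485 = 1.435 and λ(0.8) = 1.6 × 1.435 = 2.296. Power at d = 0.8 is Φ(2.296 − 1.960) = Φ(0.336) = 63.1%.

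In reverse, 80% at d = 0.8 needs λ(0.8) = 2.80 (SE = 0.2856). Then λ(0.5) = 2.80/1.6 = 1.75, and power is Φ(1.75 − 1.96) = 41.7%.

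| Test | Power at d = 0.8 if 30% at d = 0.5 (normal / 46 df / 2 df) | Power at d = 0.5 if 80% at d = 0.8 (normal / 46 df / 2 df) |
|---|---|---|
| Two-sided 0.05 | 63.1 / 63.1 / 56.5% | 41.7 / 41.7 / 48.3% |
| One-sided 0.05 | 55.9 / 55.9 / 53.0% | 46.4 / 46.4 / 50.0% |
| Two-sided 0.10 | 55.4 / 55.4 / 52.7% | 46.4 / 46.5 / 50.0% |
| One-sided 0.10 | 47.2 / 47.2 / 46.5% | 51.8 / 51.8 / 53.2% |
| Two-sided 0.01 | 76.0 / 76.0 / 59.2% | 33.0 / 33.0 / 47.0% |

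No entry in the middle column reaches 80%, and none in the last column is as low as 30%.

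**Step 3: look for an alpha that fits.** With a normal reference, 30% at d = 0.5 gives 80% at d = 0.8 when two-sided alpha is about 0.005, 84.5% at 0.002 and 87.2% at 0.001. Any alpha of about 0.005 or smaller therefore fits a claim of more than 80%. At 0.005 the SE must be about 0.22, below the 0.289 of 48 independent unadjusted patients. With 2 df, no two-sided alpha between 0.00001 and 0.05 fits.

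**Step 4: allow for rounding.** Reading the 30% as 34.9% raises power at d = 0.8 only to 71% (two-sided 0.05, normal reference).

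**The case against.** *Covariates could supply the missing power.* Section 8.3.1 plans adjustment, and more than 80% at d = 0.8 is attainable under clustering: with assumed R² = 0.50, ICC = 0.05, two-sided 0.05 and a normal reference, SE = √(2 × 1.55 × 0.50/24) = 0.254 and power is 88%. This stands as a defence of the 80% taken alone. It does not reconcile the pair, because the same SE gives 0.5/0.254 = 1.97 and about 50% at d = 0.5.

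*A reader might infer that the figure above 80% is the wrong one, from a calculation that ignored clustering.* The resemblance in Step 1 invites this, but the documents do not show how either figure was obtained. With enough covariate gain the 80% could be right; with modest clustering (ICC about 0.04 at two-sided 0.05, normal reference, no covariate gain) the 30% could be.

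*A reader might also infer that true power is far below both figures because only four oncologists are randomized.* With t on 2 df, two-sided 0.05 and no covariate gain, power at d = 0.8 would be 35%, 25% and 21% at ICC 0, 0.05 and 0.10. Those inputs are assumptions; the plan names no df method, ICC or R². They show that the choice matters, not that the plan has that power.

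*This is a pilot.* Objectives 2 and 3 concern feasibility, acceptability and preliminary efficacy; 8.1 already discloses low power at a medium effect; and no go/no-go rule depends on power. All of that stands. It limits the consequence, but not the inconsistency.

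**Conclusion.** The two power sentences are wrong as written. Taking the 30% as given, the figure above 80% is at least 17 to 27 points too high across two-sided 0.05, one-sided 0.05 and two-sided 0.10, and 80% power would be reached only at d of about 0.98 to 1.22. Taking 80% at d = 0.8 as given, the 30% is about 12 to 20 points too low across the same tests. Outside those alphas the size changes (about 47% at d = 0.8 for one-sided 0.10, about 76% for two-sided 0.01 with a normal reference), but the conflict remains.

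The result needs no assumption about ICC, R² or sample size. It needs only that both figures refer to the one design named in the sentence and to one test at a conventional alpha. It does not identify which figure is wrong, and it does not show that the pilot needs more patients.

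**What to change.** **Required, Section 8.1.** Recompute both powers from one common, stated set of assumptions that matches the planned model with oncologist as a random effect, and replace both power sentences with text such as:

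> With 4 oncologists (2 per arm) and [N] patients ([m] per oncologist), [one/two]-sided alpha [value], ICC [value or range, with source], covariate R² [value, with source] and [df method], power is [x]% for d = 0.8 and [y]% for d = 0.5.

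State whether N is 48 or the enrolment target of 50, and why.

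**Secondary and optional.** Name in 8.3.1 the df method for the arm effect and its interval, and use the same one for the power. Also soften the statement about stable estimates to say that intervals may be wide with only 4 oncologists. As an illustration on assumed inputs (ICC 0.05, no covariate gain, SE 0.359), the 95% half-width is 1.96 × 0.359 = 0.70 SD with a normal reference and 4.303 × 0.359 = 1.55 SD with 2 df.

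**Cost.** A recalculation and a rewording, with no extra patients and no change of design. The likely price is a less favourable stated power.
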